## 2- Visit1-pre clinical (around 3 hours)

All the visits for healthy subjects and ASD subjects will occur at the Emory Hospital. With the help of ACTSI facility, we will use one of their external outside CRN unit rooms to test participants on computer tasks, make interviews, collect saliva samples, filling questionnaires and getting snacks. For all the medical and health assessments (physical exam, vital signs, blood withdraw, spray intake) will occur inside the CRN outpatient services. For the MRI scan, we will conduct it at BITC scanner. All post-scanner questionnaires will be conducted in this external room provided by ACTSI inside the hospital.

## **ASD subjects**

Upon arrival, staff will review the screening form previously filled as well as eligibility criteria and the MRI screening form out for correctness and affirm that no changes in their health or medical history have occurred. If any changes have occurred, the study staff will consult with the PI or the study physician, if necessary. We will review the consent form with the subject. We will also assess his understanding of the consent by asking specific questions that are part of an assessment of capacity form. The experimenter will ask the questions to the patient and will take notes of his responses. If the patient did not answer correctly to all questions, we will review the consent again and ask the questions again to ensure a full understanding of the consent. Once the patient understands the consent, we will proceed to the signature. This assessment of capacity form will be only administered to patients with ASD and not to healthy subjects.

The nurse practitioner or the study physician will conduct a brief history and physical. The nurse practitioner will go through the inclusion and exclusion criteria again to ensure that the patient is ready to participate in the subsequent clinical visit. This health assessment will be reviewed again one more time during one of the subsequent clinical visits.

Participants will fill a family history form related to themselves and to their family history .

We will collect saliva samples (3 DNA Genotek kits) for genotyping analysis and methylation analysis.

The patient will complete several questionnaires.

Given that there is lot of questionnaires to complete, we can ask participants if they prefer to complete them at home. Participants can complete the questionnaires and bring them back during the following visits.

Participants will also perform a social learning test during which the participants match faces or words as fast as possible. This test is an adaptation of the implicit association task during which we study implicit associations.

Participants will be trained on the different behavioral tasks that they will be performing during the MRI scanner: the face perception task and the social games. There will be specific instructions and a practice session on the computer screen for each of these tasks. Participants will complete a quiz for the face perception task and for the ball-game to double check the comprehension of the task. If there are errors in responses, the experimenter will repeat the instructions or, if necessary, present some training sessions on the screen and repeat the questions that participants did not answer correctly, until he has all the answers correct.

At the end of this visit, participants will go through a brief clinical standardized interview (Bio-behavioral clinical global interview BB-CGI) with the experimenter during which the experimenter will ask questions to the subject and record their interactions.

This clinical test will be repeated at the end of each of the following 4 MRI visits in order to evaluate the progress or come up with a score of socio-emotional, verbal, physiological and clinical index of improvement.

We will take a photo from this video to keep the photo identification in the folder of the patient.

At the end of the interview, the study staff will take the patient to the BITC MRI scanner at the Emory Hospital for a practice/habituation session. The participant will lay down in the scanner (same way as described below during the clinical visits), get familiarized with the coil and the tunnel, with the response box (that he will use to answer during games), with the noise, and to with some examples of the tasks that he will perform during the actual clinical visits. We will run an fMRI sequence for few minutes (that might include a resting state, face test, ball-game). At the end of the MRI training/habituation, we will ask participants few questions about his experience. The participant will be also asked about any adverse events. In case of mild anxiety, the experimenter will make sure to give the participant time to rest and ask him if he would like to continue habituation.

Participants will also have a look at the CRN unit.

Given the complexity of scheduling MRI scanner, the CRN unit and the nurse practitioner, the tasks above do not need to be performed in a particular order. Even the health assessment can be performed at any time given that the goal of the health assessment is to make sure that the subject is healthy before its inclusion in the subsequent 4 clinical visits.

Of note, the results of the health assessment do not determine whether the subject can or cannot participate in this first non-clinical visit.

Given that the MRI scanner is always functioning, we will make sure to collect MRI screening forms from subjects before approaching the magnet.

	Screening And health assessment	Consent	DNA	Questionnaires	Computer tasks	Clinical interview	Training on behavioral tasks and MRI + questionnaire
Prior visits	X						
Pre-MRI visit	X	X	xxx	X	X	X	X

Table 1: Pre-clinical Visit 1 for subjects with ASD

### 3- Second visit: clinical visit for ASD (total duration= around 3 to 4 hours)

Subjects will meet the study staff at the Emory University Hospital. The different behavioral questionnaires, trainings and physical exams will be performed inside the hospital (in a separate room of the CRN unit). All the vitals as well as the nasal spray delivery and blood samples and DNA saliva samples will be performed inside the CRN unit in the presence of a nurse.

Given that the staff researcher needs to synchronize between MRI scan appointment, CRN unit, IDS and hormone timeline, we will be flexible with the order of administering questionnaires, training and practice sessions to participants (dependent on breaks and fatigue of participants).

Inside the scanner, participants will perform these 2 tasks:

**Task number 1: Face perception task (FPT):** participants will be given a tutorial and a short trial practice session to familiarize them with the procedure of the task. The Subjects will also complete a simple quiz to insure the comprehension of the task. If the subject incorrectly answers one or more question, the researcher or coordinator will explain why the answer was wrong and will not proceed with the experiment until convinced that the subject understands the game. During this test, we will use an eye tracker (from the SMI company) to track participants' eye movements inside the scanner.

**Task number 2: Multi-player emotion-based ball game (MP-EBG):** participants will be given instructions and a short trial practice session to familiarize them with the procedure of the game. The Subjects will also complete a simple quiz to insure the comprehension of the task. If the subject incorrectly answers one or more question, the researcher or coordinator will explain why the answer was wrong and will not proceed with the experiment until convinced that the subject understands the game.

Subjects will be asked to refrain from use of caffeinated drinks or tobacco for at least 12 hours prior the blood pressure and heart rate measurement.

- **Consent and training:** We will first review the screening and the consent form. Participants will also perform the training/practice and quizzes on the face perception task and the ball-game that will be performed inside the scanner. Participants will also be asked to complete simple questionnaire (such as the face rating questionnaire). Questions about the mood will be again asked after spray intake.
- **Vital signs:** Prior to hormone administration, temperature, heart rate and blood pressure will be measured and recorded by the CRN nurses. Weight and height will be also measured. If heart rate is above 100bpm, or blood pressure is above 140/90, vitals will be re-measured. If levels remain elevated after 3 successive recordings in both limbs (total of 6 recordings) measured at least 5 minutes apart, the study physician will be notified and asked to advise on how to treat the subject and whether it is safe to continue with the protocol. Subjects may still be included at the discretion of the study physician. This is done in order to proceed with baseline vital signs that are within post-hormone administration guidelines. Researcher will ask if the subject is experiencing any adverse events at this time, to provide a baseline before hormone administration.
- **Blood draw:** A registered nurse from the CRN will collect 10 ml of blood by venipuncture for subsequent baseline measurement of plasma oxytocin. Blood will be collected in a lavender-top EDTA-treated tube. Samples will be immediately centrifuged at 4C by the CRN core laboratory and the plasma and blood cells will be stored at -80 until assay at the CRN unit.
- **Spray intake:** Patients with ASD will receive intranasal administration of either syntocinon oxytocin spray 8IU or 24IU or 48IU or placebo. Given that it is a double blind study, we will make sure that all participants receive the same amount of puffs (12 total puffs) across all visits across all doses and placebo. Nurse will instruct the patient to clear the nose from obvious obstruction before administration. The nurse will prime the bottle by spraying in the air before administration. The nurse instructs the subject to sit with the head upright with little tilting to the back. The patient can close one nostril with one finger while the nurse is administering the spray to the other nostril. The nurse will ask the patient to sniff and breathe in gently directly after each delivery and block the opposing nostril. The insertion depth of the spray should be greater than 1.5 cm into the nostril. Ideal is around 1 cm. The nurse will hold the bottle on angle > 45 degrees from tip of spray bottle to horizontal plane. The nurse will make sure that the correct amount was entered and that there is no drainage from the nose. We are adding an appendix on chemistry and design at the end of this protocol to provide more details on the drug design. The placebo solution will contain all the inactive ingredients of the OXT solution except for the active oxytocin neuropeptide. The placebo and the Syntocinon spray will be purchased from a pharmacy in Switzerland. Both the experimenter and the subject will be blind to the solution they are receiving. Nurses will be trained on the instructions for the application of the nasal spray. They need to make sure that they depress the lever until the subject feels the mist of spray in the nostril and then let them breathe in deeply through the nose and afterwards to place

the applicator in the other nostril and repeat the process with some few seconds interval. Subjects will be asked to answer some questions on whether he could discriminate the different doses of oxytocin or oxytocin from placebo. Participants will be asked on whether they think they took placebo or oxytocin following spray intake. A stopwatch will be started at the middle of the administration of the spray so that the resting state fMRI starts exactly at 40 minutes later.

Healthy subjects will only receive 12 puffs of placebo spray. They will not receive Syntocinon spray. However, they believe that they might be taking placebo or Syntocinon.

- **Blood draw:** 5 minutes after spray intake, a registered nurse from the CRN will collect 10 ml of blood by venipuncture for subsequent baseline measurement of plasma oxytocin. Blood will be collected in a lavender-top EDTA-treated tube. Samples will be immediately centrifuged at 4C by the CRN core laboratory and the plasma and blood cells will be stored at -80 until assay.
- **Vital signs:** 15 minutes after spray intake, temperature, heart rate and blood pressure will be re-evaluated by the CRN nurse to check for any side effects of IN-OT. There are several pieces of evidence of safety and absence of side effects from chronic and acute intake of IN-OT. Thus, we do not expect any side effects from the hormone oxytocin intake. However, we will ask subjects if they feel any side effects. If no side effects are reported, but temperature has increased or decreased more than 2 degrees, heart rate is above 100 bpm, or blood pressure is above 140/90, the vitals will be re-measured. If levels remain elevated after 3 successive recordings in both limbs (total of 6 recordings) measured at least 5 minutes apart, the study physician will be notified and asked to advise on how to treat the subject and whether it is safe to continue with the protocol. Subjects may still be included at the discretion of the study physician. If subjects were to experience a serious adverse event, such as a heart attack or an anaphylactic reaction, a code will be called and, if necessary, the subject will be taken to the Emory ER. [name] or/and [name] and the CRN nurses will be notified by the experimenter. [name] or [name] will call to admit the subject to the ER. As we already mentioned, it is not likely that oxytocin has any side effects based on the growing evidence in the literature. In addition to vital signs, we will ask participants if they feel any side effects.
- **MRI scanner (one-hour duration):** Subjects will next be escorted to the Biomedical Imaging Technology Center in Emory University Hospital from the CRN, accompanied by study staff. Subjects will next be positioned in the MRI scanner (Siemens, 3T). Subjects will lay motionless inside. Padded head restraint will minimize head movement during scanning. Each scanning session will begin with a scan to localize the position of the brain within the magnet. A vitamin E capsule will be taped to the subjects left temple as a localizer for the images collected. Participants will be given a button box which they will use to perform all the tasks. We can also give them a blanket if they are cold. We will explain to participants how to use the box for each of the tasks. Before starting the tasks below, we will run localizer sequence.

- **At first, (40 minutes after spray intake)** participants will be asked to rest and not think of something specific for 8 minutes. We will be recording brain activity during resting state (no task involved).
- **Second, (FPT or face perception task)** participants will be told that faces will be presented at the screen and that these faces will be separated by a fixation cross that can be blue or red. They are asked to press a key whenever they observe a blue cross. During this task, participants' eye movements will be recorded by an eye tracker that will be implemented inside the MRI scanner. Participants will not be told about the eye tracker given that we don't want to bias their attention. Participants will be wearing the watch sensor. Participants will be debriefed about the presence of the eye tracker at the end of the study.
- **Third, (MP-EBG or multi-player's emotion-based ball game)** participants will play several runs of the ball game with several players. We might have a discussion that will be shown at the screen with another coordinator to convince participants that they are playing with other players that are staying in another room. Participants were already instructed about the details of the game.
- **Anatomical Image Acquisition:** Field map and T1 will be acquired (this can be acquired in the middle in between games or at the end of the session).
- **Post MRI scan:** Subjects will be escorted to the office next to the scanner and will be asked to rest and then complete some tasks and questionnaires. It is possible that we offer participants some snacks or lunch. Participants will complete:
  - **Face Rating questionnaire (post MRI):** participants are asked to rate (on a scale 1 to 7) faces.
  - **A social learning test (SLT):** participants are asked to match faces and words as fast as they can.
  - **Emotion Matching test (EMT):** participants are asked to identify the emotion that is displayed on a face by matching the emotional face that appears on the left to one of the faces that appears to the right (different faces but same emotion).
  - **Toronto Alexithymia scale:** participants are asked to complete a simple questionnaire.
  - **Mood questionnaire (PANAS scale).**
  - **BB-CGI (clinical interview):** the same interview that is performed during the pre-MRI visit will be performed during this visit in order to collect a clinical score of improvement as well as physiological, verbal and socio-emotional improvements.

4- Second, Third and Fourth visit of scan (ASD subjects) (total duration= around 3 to 4 hours each): The exact same procedures will be performed during these other 3 visits. These 3 additional visits will be conducted only in ASD subjects. Also, participants will receive different content of spray (either different dose of oxytocin or placebo).

Of note, the health assessment will be reviewed one more time (in addition to the assessment during the first pre-clinical visit) by the nurse practitioner or the study physician during one of the 4 clinical visits, if the original health assessment expires (more than 30 days).

	Screening and consent review/training	Vital signs 1	Blood samples Pre	Hormone Spray (PL, 8, 24, 48 IN-OT)	Blood samples post	Vital signs 2	MRI scan	Post MRI scan
Visit 1	X	X	X	X	X	X	Rest+ 3 tasks	Quest+ 2 tasks + clinical interview
Visit 2	X	X	X	X	X	X	Rest+ 3 tasks	Quest+ 2 tasks + clinical interview
Visit 3	X	X	X	X	X	X	Rest+ 3 tasks	Quest+ 2 tasks + clinical interview
Visit 4	X	X	X	X	X	X	Rest+ 3 tasks	Quest+ 2 tasks + clinical interview

Table 2: Clinical trial visits for subjects with ASD

Visits will be separated by a one-week interval approximately ( $\pm$  2 to 3 days). We have to be flexible with the scheduling given that we are facing challenges while scheduling all the units and personals. Every patient will receive the 3 doses of IN-OT (8IU, 24IU, 48IU) and placebo in a double blind, placebo controlled trial.

It is also possible that some patients will feel tired and will not be able to go through all the tests inside the MRI scanner. In this case, we will stop as based on participants' level of fatigue. We will try to have similar number of tests across 4 clinical visits.

I would like to mention here that given the complexity of this study, we expect that some of the tasks/procedures will be omitted or not completed during each of the 5 visits. We do not expect that all patients perform all the tasks described above (inside or outside the MRI scanner). We will try our best to test participants on all these tasks above but we could face some challenges and decide not to complete them. For instance, we will be based on the fatigue level of patients and patients' feedback to make these decisions. The level of fatigue varies from one participant to another.

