We hypothesize that high levels of IN-OT will enhance brain activity and functional connectivity of social brain networks areas involved in perception and emotional processes in response to dynamic social cues as compared to non-social cues. We are also interested in looking into the effects of IN-OT on reducing the activity of amygdala and anterior hippocampus in a context dependent fashion (as based on level of stress). We also believe that the clinical/behavioral and endophenotypes will play a fundamental role in determining OXT's effects on brain activity.

Primary outcome measure: Here, we are looking to differences between treatments conditions on BOLD activity of perceptual and emotional brain regions while participants play a multi-player ball game. We predict that a higher dose of IN-OT will enhance the BOLD activity of reward brain regions (such as OFC, ventral striatum, Nucleus accumbens, ventral tegmental area) and perceptual brain regions (such as inferior occipital, fusiform gyrus, superior temporal sulcus, amygdala, superior parietal lobe) and insight awareness (insula and ACC) for facial expressions as compare to neutral non-social trials, *regions that are expected to be less activated in placebo as compared to healthy subjects*. We also expect increased activity in rewarding brain regions in response to positive social feedback as compared to neutral social feedback. We also expect to find a main effect of IN-OT on reducing the activity of amygdala and hippocampus during the ball-game, in a context dependent manner (which could be related to a reduction of stress and anxiety). Indeed, we expect to find the neutral feedback trials to be more stressful and activating more the amygdala when compared to the positive trials.

Indeed, in contrast to positive feedback, we expect the neutral to be eliciting negative social feedback in this kind of social context.

Secondary outcome measure:

We are looking into differences between treatment conditions on behavioral outcome of social learning paradigm (post scanner) following the ball-game. We are looking into implicit effects of learned emotional associations on reaction time. We expect to find more emotional implicit social biases with IN-OT.

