*The secondary outcome measure* consists of correlating the effects of treatments on rsFC with the clinical improvements following treatments and post scan in ASD. The variables consist of BB-CGI clinical score (that will be rated blindly by a physician) and a socio-emotional behavioral score (rated by PI or staff blindly) during the BB-CGI. These two variables will be analyzed separately as they are dependent (based on the same test) but answer two different questions. We will conduct correlation analysis (Spearman or Pearson) between TEE-OXT or OXT-effect on rsFC and behavioral and clinical improvements. Behavioral variables will include: emotional responses, gestures, eye contact with experimenter and synchrony).

**For aim 2:** *The primary outcome measure of the second aim* consists of investigating the differences between the effects of the different treatments on BOLD activity of socio-emotional brain regions in response to social cues (Face perception task) in ASD. ROI analysis will include regions such as inferior occipital cortex, fusiform gyrus, superior temporal cortex, intra-parietal sulcus, superior parietal lobule, nucleus accumbens, amygdala and OFC). In this analysis, we have two variables that we will contrast (BOLD signal in response to emotional faces versus

neutral faces) and 4 treatment conditions within subject design (8IU, 24IU, 48IU and placebo) with covariates (order of visits to control for familiarity effects given that the treatment conditions are completely randomized). The presence of TEE-OXT will consist of finding differences between different treatment conditions of OXT and not only between OXT and placebo. We will also compare each of these OXT treatments with placebo condition separately to study OXT-effect.

*The secondary outcome measure* will consist of studying the effects of different treatments on a behavioral measure that is recorded during the MRI scan of the FPT: visual fixation duration on facial stimuli. Here, we have one variable (duration of visual fixation or eye gaze on emotional and neutral faces) and 4 treatment conditions. We will analyze the data with ANOVA repeated measures for determining TEE-OXT and t-tests for simple OXT-effects.

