**For aim 3:** *The primary outcome measure* of the third outcome measure consist of studying the different effects of treatments on BOLD activity of key brain regions (OFC, ventral striatum, inferior occipital cortex, fusiform gyrus, amygdala, superior parietal lobe, insula and ACC) while playing a social interactive ball-game in ASD. During this ball-game, we will analyze the BOLD brain activity during social output videos that will display either neutral or positive face expressions. We expect more rewarding brain regions to be more activated during the process of positive social feedback with oxytocin treatment. In order to determine TEE-OXT, we will conduct repeated ANOVA analysis with variables (BOLD activity in response to positive and neutral) and treatments (8, 24, 48, placebo). We will also investigate the general effect of TEE-OXT on the BOLD activity of socio-emotional brain regions in response to both positive and neutral faces with the variable (BOLD activity in response to all faces) and treatments. We will also investigate the differences between oxytocin treatment and placebo. We expect at least the doses of 24IU and 48IU to be different from placebo. Covariates such as visit order will be entered in the GLM model as a regressor to control for habituation effects.

*The secondary outcome measure* consists of studying the effects of treatments on behavioral outcome measure (post scanner on social learning). In this behavioral task, we will analyze the accuracy and reaction time in recognizing faces as familiar. We will conduct ANOVA and t-tests to compare the performance in these 2 variables (accuracy and reaction time) between the 4 treatment conditions.

**For aim 4:** *The primary outcome measure* of the fourth outcome measure consists of investigating the differences between treatments on the modulation of brain activity of reward brain regions in response to punishment and helpful behavior. In the GLM model, we will conduct an ANOVA or t-tests with 4 treatment conditions and the BOLD signal in NAcc, OFC, VTA and ACC.

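### If faces are reused across the four dosing visits, retained learning pulls the Aim 3 social learning contrasts toward zero, and the planned analysis has no term for it

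*Combined protocol and SAP*

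**What the plan says.** The section on the second to fourth scan visits of ASD subjects says: "The exact same procedures will be performed during these other 3 visits". The only change it names is the content of the spray. Visits are about one week apart. Appendix B lists the ball game and the social learning test at every dosing visit (visits 2 to 5).

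Objectives, Aim 3, makes the secondary outcome the "behavioral outcome of social learning paradigm (post scanner) following the ball-game", and adds: "We are looking into implicit effects of learned emotional associations on reaction time". The Statistical analysis section, aim 3, words it differently: "we will analyze the accuracy and reaction time in recognizing faces as familiar". Under either description the outcome is something learned about faces.

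The planned analysis of this outcome is: "We will conduct ANOVA and t-tests to compare the performance in these 2 variables (accuracy and reaction time) between the 4 treatment conditions". No visit, period or prior-dose term is named. Visit order is named for the imaging analyses: for Aim 2, "order of visits to control for familiarity effects given that the treatment conditions are completely randomized", and for the Aim 3 BOLD outcome, "Covariates such as visit order will be entered in the GLM model as a regressor to control for habituation effects".

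At the pre-clinical visit, before any dose, the ASD subjects section says: "Participants will also perform a social learning test during which the participants match faces or words as fast as possible".

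The documents do not say whether the players, the faces or the test items are reused or replaced between dosing visits. The different faces mentioned for the Emotion Matching test are different within an item, not between visits.

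**The concern.** A one-week gap can clear the drug, but it does not clear memory. In a four-period crossover whose outcome is learning, a patient on placebo at a late visit may still show associations formed under oxytocin. By the last visit every patient has had all four treatments. If the stimuli are the same, each score after the first dosing visit mixes today's dose with the doses that came before.

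The plan expects familiarity and habituation across visits, but provides for them only in the imaging analyses. A visit-order term removes the average practice effect. It does not remove a carry-over that depends on which doses came earlier. A null result on social learning could then come from the design or from oxytocin, and the planned analysis could not tell the two apart.

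**Working it through.** **Inputs.** Four treatments per patient in random order (Randomization and blinding; Aim 2 analysis). Expected behavioural effect d=0.32, 95% interval 0.18 to 0.47 (Statistical analysis). The team believes it can test 30 patients and plans for 50 (Randomization and blinding). Not stated, so assumed: all 24 orders equally likely; two-sided alpha 0.05; d read as a standardised paired difference; retained share L from 0 to 1.

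**The plan's own figure.** The documents give no carry-over or attenuation figure to reproduce. Their power statement (50 patients, 95%, d=0.2) depends on an unstated correlation between visits. It is a separate matter and is not used here.

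**Step 1: additive persistence to all later visits.** Let a and b be the effects of two treatments. Each score is the current effect plus L times the sum of earlier effects. In a random order:
- b comes before a half the time and adds L·b/2 to the mean score under a;
- a comes before b half the time and adds L·a/2 to the mean score under b;
- any third treatment precedes each of them equally often and cancels.

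Expected contrast = (a - b) + L·b/2 - L·a/2 = (a - b)(1 - L/2).

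| L | Share of true contrast kept |
|---|---|
| 0 (new faces, or nothing retained) | 1.00 |
| 0.25 | 0.875 |
| 0.5 | 0.75 |
| 1 | 0.50 |

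Fitting patient and treatment effects over all 24 orders gives the same shares with or without a visit term. At L=1 the contrast is 1, 2/3, 1/3 and 0 of its true size at dosing visits 1 to 4, which averages 2/4 = 0.50.

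**Step 2: other forms of persistence.**
- Next visit only: b immediately precedes a in 6 of 24 orders, so the factor is 1 - L/4. At L=1 it is 0.75, a loss of at most 25%.
- All patients at ceiling after the first dosing visit: only that visit carries the contrast, so 1/4 is kept.
- First-visit learning retained unchanged: 0 is kept.

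**Step 3: power.** Paired t-test, noncentrality = d × √n. For n=30, √30 = 5.48.

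| L | d after shrinkage | d × √30 | Power, n=30 | Power, n=50 |
|---|---|---|---|---|
| 0 | 0.32 | 1.75 | 40% | 60% |
| 0.5 | 0.32 × 0.75 = 0.24 | 1.31 | 25% | 38% |
| 1 | 0.32 × 0.50 = 0.16 | 0.88 | 14% | 20% |

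**Step 4: what analysis can recover.** With visit terms and an indicator for each treatment already received, the full contrast is recovered in expectation if the additive model holds. Over the 24 orders the variance factor of a contrast rises from 0.083 to 0.208, and 0.208/0.083 = 2.5. The effective d is then about 0.32/√2.5 = 0.20, and power with 30 patients is about 19%. The model removes bias but does not restore power.

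The first dosing visit alone is free of carry-over from earlier doses. It is a between-patient comparison of 30/4 = 7.5 patients per treatment, with about 9% power at d=0.32.

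**The case against.** The strongest reply is that the premise is not written down. Identical procedures need not mean identical stimuli, and different players or faces within the same task would fit the wording. That the faces tested are the game faces is also inferred, because the analysis section does not name them. A reader might infer that the plan reuses the same faces and that carry-over is therefore established. The documents do not support that: reuse is the natural reading, but no passage states it. This part stands, and the point is conditional for that reason.

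Three further objections stand in part.
- The pre-clinical social learning test comes before any dose, so it cannot carry a dose effect forward and adds nothing to the argument.
- The section on screening healthy subjects says that all the ASD patients have already been run, so new face sets cannot help existing data.
- At d=0.32 and 30 patients, power is only 40% even without carry-over, so a null would be likely anyway.

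The last does not dispose of the point. Low power and bias toward zero are different faults, and only the first is visible in a confidence interval.

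**Conclusion.** The point holds in conditional form. Unless face sets differed between dosing visits, the Aim 3 social learning contrasts are biased toward zero, and the planned ANOVA and t-tests neither prevent nor detect it. Under additive persistence to all later visits, 75% of the contrast remains at L=0.5 and 50% at L=1. Power with 30 patients falls from 40% to 25% or 14%, given d=0.32 as a paired difference and two-sided 0.05.

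Two stronger readings are tempting. One is that half is the most that can be lost. That belongs to the additive model only: the loss is nil with new faces, at most 25% if only the next visit is affected, and 75% to 100% under the ceiling and first-visit-retention models. The other is that every dose contrast in the trial is affected. The working concerns one behavioural secondary outcome; nothing here shows the same for the imaging, gaze or plasma outcomes.

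**What to change.** State in the protocol whether the game faces and the social learning items were the same at all four dosing visits. If they differed, the point falls away.

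In the Statistical analysis section, aim 3 secondary outcome:
1. Add visit order to the model for accuracy and reaction time.
2. Add a sensitivity model with terms for the doses received at earlier visits. The cost is about 2.5 times the contrast variance, and it relies on the additive model.
3. Report the first-dosing-visit estimate beside the four-visit result, descriptively only, given about 7 to 8 patients per treatment.
4. State that, if faces were reused, a null four-visit contrast may reflect retained learning.

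These cost one extra model and a few sentences. The plan already says that further analysis detail will come by amendment.

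For any patients added later (Randomization and blinding mentions possibly 50 more), use a matched face set with matching test items for each dosing visit and rotate the sets across doses. The cost is three extra sets and a rotation list. Small differences between sets are balanced by the rotation.
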